6.6. Nerve Conduct Test Analysis Windows

Per protocol, if the repeated per-protocol nerve conduction test performed on the regions of the peroneal, sural, or ulnar nerves at any post-baseline visit shows a difference from baseline of >12%, up to 2 unscheduled tests will be repeated at the same nerve.

The following visit windows will be used to map the unscheduled visits of the unscheduled NCT tests, based on the study day:

Visit	Targeted Study Days*	NCT Analysis Window in Study Days
Screening	Day -30 to Day -11	≥ -30 and ≤ -11
Pre-randomization	Day -10 to -7	-10 to -1
Baseline	1	≤ 1
Week 8	57	[29, 85]
EOT Week 16	113	[86, 183]
Week 36	253	≥ 184

*Study days are calculated from the first dose of study drug (Day 1).

If multiple measurements occur within the same visit window, the last one within the window will be used in the analysis.

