7.3.2.1. Reasons for Permanent Discontinuation of Study Drug

Study drug dosing will be permanently stopped in the event of:

- A patient developing clinically significant peripheral sensory or motor neurologic events confirmed by a neurologist's examination and graded by the neurologist as at least moderate peripheral neuropathy limiting activities of daily living, ie, grade ≥2 according to Common Terminology Criteria for Adverse Events (CTCAE) v.4; study sites should use CTCAE v.4 criteria throughout the study for consistency
- Evidence of pregnancy

- A patient developing signs and symptoms indicative of carpal tunnel syndrome
- Continued noncompliance with protocol-defined maximum acetaminophen/ paracetamol use (with a maximum daily dose of 2500 mg [countries where 500 mg strength tablets/capsules are available] or 2600 mg [countries where 325 mg strength tablets/capsules are available]) during the treatment and follow-up periods, after appropriate counseling
- Continued noncompliance with the protocol, including usage of NSAIDs or other medications or non-pharmacologic treatments that are not permitted in the study, after appropriate counseling
- JR surgery
- AESI:
 - Adjudicated arthropathy, as described in Section 9.6.1.1.
 - Sympathetic nervous system dysfunction, as described in Section 9.6.1.2.
- Per protocol repeated nerve conduction test that confirms results are not within the established parameters for peroneal, sural, or ulnar nerves, as per central reader assessment and the neurologist's evaluation that confirms the diagnosis of peripheral neuropathy.
- Hepatotoxicity. Study drug should be discontinued if the following are observed:
 - 1. Total bilirubin (TBL) >2x ULN or international normalized ratio (INR) >1.5, and
 - 2. ALT or AST >3x ULN, and
 - 3. No other cause for 1 and 2 is readily apparent

Other causes of ALT, AST, and TBL elevations may include alcoholic hepatitis, autoimmune hepatitis, non-alcoholic hepatitis, heritable diseases (Gilbert's Syndrome), heart failure, and viral hepatitis.

NOTE: Study drug may be withheld in patients who do not meet criteria for permanently discontinuing study drug, until an alternative cause for drug-induced liver injury can be determined. The patient may be re-challenged if an alternative cause for elevated liver function tests is found and the liver function tests return to baseline, but only after discussion with the sponsor.

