9.6.1.3. Peripheral Sensory Adverse Events

Altered peripheral sensation (eg, paraesthesia and hypoaesthesia) is an important identified risk with fasinumab (see Investigator's Brochure) and other anti-NGF compounds. Any peripheral sensory AE that, per the investigator's judgment, requires a neurology or other specialty consultation must be reported as an AESI. If any peripheral sensory event persists for 2 months, the patient must be referred for a neurology or other specialty consultation and the event must be reported as an AESI. Refer to the study manual for further details related to reporting of peripheral sensory neuropathy AEs.

If the repeated per-protocol nerve conduction test performed on the regions of the peroneal, sural, or ulnar nerves at any post-baseline visit shows a difference from baseline of >12% (based on central reader assessment), the patient will be referred for a neurology evaluation. If the neurologist's evaluation confirms the diagnosis of peripheral neuropathy, the study drug will be permanently discontinued. Refer to the study manual for further details related to reporting of results of nerve conduction tests.

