10.2. Justification of Sample Size

Approximately 180 patients will be randomized in a 1:1 ratio to fasinumab 1 mg Q4W or placebo.

With this sample size, the precision of the estimated treatment difference between fasinumab and placebo at week 16 in nerve conduction velocity is no more than 1.21 m/s with a 95% confidence level, assuming a standard deviation (SD) of 3.6 m/s. This sample size provides similar precision for the estimated treatment difference in nerve conduction amplitude assuming an SD of 3.6 μ V. The assumed SDs are estimated based on the nerve conduction results from Arezzo 2008.

Assuming a 2-sided alpha level of 0.05 and a 15% dropout rate up to week 16, an enrollment of 90 patients per group will provide at least 80% power to detect an effect size of 0.46 in the WOMAC pain and physical function subscale scores (ie, absolute treatment difference of 1.1 between fasinumab and placebo with an SD of 2.4). The assumed treatment difference and SD are based on results from study R475-PN-1227.

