5.8.1. Primary Safety Analysis

The variables for the evaluation of peripheral nerve function are the change from baseline to week 16 (based on central reader assessment) in the amplitude and velocity from the 3 individual nerve conduction tests.

The nerve conduction variables will be analyzed using an MMRM approach based on the safety analysis set. The model will include baseline value, randomization strata, treatment, visit, and treatment-by-visit interaction. The least-squares mean estimates for the mean change from baseline to week 16, as well as the differences of the estimates between fasinumab and placebo, with their corresponding standard errors and associated 95% confidence intervals, will be provided descriptively.

No imputation will be made for Nerve Conduction values that were missing as a result of technical error, were not performed, or performed outside of scheduled visit windows. For measurements recorded as physiologically absent ("No Response", meaning outside detection sensitivity of the test), nonzero values were imputed using the 1st percentile of all non-missing values across all visits, all patients, and all treatment groups. This will be done to impute the low end of the range of detectable values while avoiding undue influence by outliers.

Data collected after discontinuing treatment up to week 16 will be included and used in the primary safety analysis. Any unscheduled repeated NCT tests data outside the window described in Section 6.6 will not be used in the primary safety analysis, but used in a sensitivity analysis.

Sensitivity Analysis

Sensitivity analyses will be performed to assess the robustness of the results generated for the primary safety variables.

Sensitivity analysis for the primary safety endpoints will be performed using similar analysis method as the primary safety analysis. For the unscheduled repeated tests at week 8, week 16 and week 36, the window described in Section 6.6 won't be used. Alternatively, the last test value prior to the next scheduled visits will be used in this sensitivity analysis. Missing nerve

conduction variables up to week 16 will be imputed using the same approach used in the primary analysis.

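### For any nerve measure the 12% trigger covers, the SAP's last-repeat rule can understate a stable or recovering drug effect at week 16, and no planned analysis keeps the scheduled value of a patient retested within the window

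*SAP*

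**What the plan says.** The primary endpoints are the changes from baseline to week 16 in velocity and amplitude for the peroneal, sural and ulnar nerves. They are analysed by MMRM, and Protocol 10.1 limits them to estimates with 95% intervals, without a formal test.

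SAP 6.6 says that when a test differs from baseline by more than 12%, "up to 2 unscheduled tests will be repeated at the same nerve". It assigns unscheduled tests to windows (week 8: Days 29 to 85; week 16: Days 86 to 183; week 36: Day 184 onward) and adds: "If multiple measurements occur within the same visit window, the last one within the window will be used in the analysis". The scheduled Day 113 test lies in the week 16 window.

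SAP 5.8.1 carries this into the primary analysis by excluding only what falls outside: "Any unscheduled repeated NCT tests data outside the window described in Section 6.6 will not be used in the primary safety analysis". The sensitivity analysis drops the windows: "Alternatively, the last test value prior to the next scheduled visits will be used in this sensitivity analysis".

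Protocol 9.6.1.3 uses the same 12% figure for patient care: a test that "shows a difference from baseline of >12% (based on central reader assessment), the patient will be referred for a neurology evaluation". Neither section says whether the 12% refers to velocity, amplitude or both. Both speak of a repeated per-protocol test, so it is also unclear whether one scheduled reading or an already repeated test is the trigger. The limit of two repeats appears only in the SAP, and the protocol sends procedural detail to the study manual.

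**The concern.** Only readings far from baseline are redrawn; unremarkable readings stand. Whether a value is replaced therefore depends on the value itself. If fasinumab slows conduction, more fasinumab patients cross the trigger on the low side. Part of each extreme reading is test error, so the repeat moves back toward the patient's true value. The arms are then treated unequally and the difference shrinks. If the nerve has partly recovered by the repeat, the loss is larger.

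The rule also departs from the SAP's own conventions. SAP 6.5 takes the value closest to the target day when several share a window, and SAP 6.7 takes the first laboratory value.

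At stake is the reported estimate in a neurological safety study. With no formal test, the estimate and its interval are the primary result, and for a stable or recovering effect the error runs toward no harm. The planned sensitivity analysis uses the same kind of rule, so it cannot show the shift.

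**Working it through.** **1. The plan's own figure.** The inputs in Protocol 10.2 are 90 per group and a normal-theory interval, "assuming a standard deviation (SD) of 3.6 m/s". Half-width = 1.96 × SD × √(2/n).
- n = 90: 1.96 × 3.6 × √(2/90) = 1.05 m/s.
- n = 76 (the 15% dropout that the plan gives for WOMAC): 1.14 m/s, or 1.15 using t.
- n = 76 with an 80% tolerance probability on the sample SD: 1.208, which rounds to the stated 1.21.

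The stated bound is met.

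**2. Timing.** The last dose is scheduled for Day 85, and the window closes 183 − 85 = 98 days later. This is a ceiling, because the documents do not say when repeats are done.

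**3. Assumptions for size (none is in the documents).** Velocity triggers the repeat on one scheduled reading, in either direction. Mean baseline is B = 40 to 50 m/s, and the true effect is μ = −1.0 m/s on fasinumab and 0 on placebo. Tests have equal normal error and share one baseline, so the correlation ρ between the scheduled and repeat changes is at least 0.5. At ρ = 0.5, all the variation in change is test error.

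The 3.6 m/s is not stated to be an SD of change. It comes from a trial in painful diabetic neuropathy, whereas exclusion criterion 9 removes patients with neuropathy. Smaller values are therefore also shown.

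**4. Formula, one repeat.** With c = 0.12 × B, X the scheduled change, S its SD and μR the effect at the repeat:

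E[analysed change] = μ + (μR − μ) × P(|X| > c) + (ρ − 1) × S × [φ((c − μ)/S) − φ((−c − μ)/S)]

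For μ = μR = 0 the expression is zero, so there is no bias without an effect.

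Worked case, stable effect, B = 45, S = 3.6, ρ = 0.5: c = 5.4, φ(6.4/3.6) = 0.082, φ(−4.4/3.6) = 0.189. The last term is (−0.5)(3.6)(0.082 − 0.189) ≈ +0.19. The expected estimate is −0.81 instead of −1.00, a loss of 19%.

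**5. Attenuation of a stable 1.0 m/s effect**

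| Case | B = 40 | B = 45 | B = 50 |
|---|---|---|---|
| S = 3.6, ρ = 0.5 | 21.5% | 19.2% | 16.5% |
| S = 3.6, ρ = 0.7 | 12.9% | 11.5% | 9.9% |
| S = 3.6, ρ = 0.9 | 4.3% | 3.8% | 3.3% |
| Test SD 2.0 (S = 2.0√2), ρ = 0.5 | 16.0% | 12.5% | 9.2% |
| Test SD 1.5, ρ = 0.5 | 7.5% | 4.5% | 2.4% |
| Test SD 1.0, ρ = 0.5 | 0.8% | 0.2% | 0.1% |

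At S = 3.6, 10-18% of placebo and 11-20% of fasinumab patients would be retested.

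**6. Other scenarios at S = 3.6, ρ = 0.5.** If half the effect is gone by the repeat, the loss is 22-32%. A second repeat when the first is still beyond 12% (an assumed rule) gives 21-30% for a stable effect. The bias reverses if the effect at the repeat exceeds 2.1 to 2.5 times the scheduled effect, or 1.2 to 1.3 times at ρ = 0.9.

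**7. Interval and error.** Simulation: baseline-adjusted, trigger on each patient's own baseline, one repeat, B = 45, test SD 2.55 (so S ≈ 3.6), between-patient SD 4, 76 per arm.

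| | Scheduled value | Last repeat |
|---|---|---|
| Residual SD | 3.33 | 2.82 |
| Half-width (m/s) | 1.06 | 0.90 |
| RMSE, true difference 1.0 | 0.54 | 0.50 |
| RMSE, true difference 1.5 | 0.54 | 0.54 |
| RMSE, true difference 2.0 | 0.54 | 0.60 |
| Coverage of the nominal 95% interval, 1.0 | 95% | 93% |
| Coverage, 2.0 | 95% | 87% |

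With test SD 1.5, coverage under the last-repeat rule is 95% and 93%.

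**8. If velocity is not the trigger.** When retesting is independent of velocity (15% retested), velocity attenuation is 0%.

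**The case against.** The strongest reply is that a confirmatory repeat filters technical noise. Protocol 7.3.2.1 relies on one for a decision about the individual patient: "Per protocol repeated nerve conduction test that confirms results are not within the established parameters for peroneal, sural, or ulnar nerves". Normal errors may also overstate the harm. If SD of change stays at 3.6 but 5-10% of tests are assumed to be noisy, attenuation is 5-9%, and the last-repeat rule has the lower RMSE even at a true difference of 2.0 (0.42-0.47 against 0.54). This stands as a reason not to insist on a new primary value. It does not justify having no analysis on scheduled values, because a repeat used to manage one patient need not be the value for a group comparison.

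The documents do not support four stronger readings that a reader might infer:
- *The velocity estimate is certainly biased.* The trigger parameter is not named, and step 8 shows no attenuation if velocity is not part of it.
- *About a fifth of the effect is lost.* The 17-22% is the upper end for one repeat of a stable effect, with the whole 3.6 m/s treated as test error.
- *Scheduled values of retested patients are never analysed.* A week 16 repeat after Day 183 leaves the scheduled value in the primary analysis. Protocol 10.4.4 also provides for nerve conduction data to be listed.
- *Repeats come months after dosing.* Day 183 only limits the mapping; nothing shows that repeats are delayed or that nerves recover by then.

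**Conclusion.** The point holds in a limited form. An in-window repeat replaces the scheduled value in the primary analysis, and the only planned sensitivity analysis on repeats also takes the last test. For any parameter the trigger covers, a stable effect is understated if tests have error, and recovery by the repeat adds to the loss. The interval is then narrower and off-centre. There is no bias if there is no effect, and growth of the effect after the scheduled test can reverse the direction.

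The size cannot be determined from the documents. Under the step 3 assumptions, one repeat of a stable 1.0 m/s effect loses between 0-1% and 17-22%, at most about 0.22 m/s. No amplitude figure is claimed.

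Severity is minor to moderate: the endpoints are descriptive, and neurology referral and the stopping rules do not depend on which value is analysed. A reader might conclude that the primary value must change. The RMSE figures do not require that, since for small effects the choice trades bias against variance.

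**What to change.** **Add to SAP 5.8.1** a pre-specified sensitivity analysis using the scheduled central-reader value at weeks 8, 16 and 36. If that test is missing or a technical failure, use the valid test closest to the target day within the existing 6.6 window. The fallback avoids losing usable data, because the SAP states: "No imputation will be made for Nerve Conduction values that were missing as a result of technical error, were not performed".

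**Report** retest counts by arm, nerve and visit.

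**State** whether the 12% trigger applies to velocity, amplitude or both, and whether one scheduled reading or an already repeated test sets it off. State also whether the next scheduled visit in the sensitivity rule means the next clinic visit (week 26 after week 16) or the next nerve conduction visit (week 36).

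The cost is SAP wording and one re-derived dataset from data already collected, with no loss of precision in the primary analysis.

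**Optional:** make the scheduled value primary and move the last-repeat rule to the sensitivity analysis. This removes the bias but widens the interval by 0-21% across baselines of 40 to 50 m/s and test SDs of 1.0 to 2.55. In the simulated case, 1.06/0.90 = 1.18, or 18%. Without baseline adjustment the half-width is about 1.15 m/s at 76 per arm, still within the stated 1.21.

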6.7. Unscheduled Assessments

The determination of baselines and values at the EOT for both efficacy and safety variables will be based on scheduled available assessments and unscheduled available assessments.

Extra assessments (laboratory data or vital signs associated with non-protocol clinical visits or obtained in the course of investigating or managing AEs) will be included in listings, but not

summaries. If more than 1 laboratory value is available for a given visit, the first observation will be used in summaries and all observations will be presented in listings.

7. INTERIM ANALYSES

No interim analysis will be performed for primary safety and efficacy endpoints. For the first DBL, all patients have had the chance to complete the 16-week treatment period but some patients have not completed the 36-week follow-up period. All data up to the first DBL cutoff date will be included in the analysis.

8. SOFTWARE

All clinical data analyses will be done using SAS Version 9.4 and above.

10. APPENDIX

10.1. Schedule of Events

Study assessments and procedures are presented by study period and visit in [Table 1](#).

Table 1: Schedule of Events

Study Week	Screening/Pre-randomization		Treatment Period							ET ¹ / JR Pre- Op	Follow-up Period			EOS Wk 64 449 ±7 Phone 1
	Screen Up to 30 Days	Pre- rand 7 to 10 Days	Baseline 1	Wk 1 8	Wk 2 15	Wk 4 29	Wk 8 57	Wk 12 85	EOT Wk 16 113		Wk 26 183	Wk 36 253	ET ¹ / JR Pre- Op	
Study Day				±1	±3	±7	±7	±7	±7		±7	±7		
Visit Window (days)														
Visit/Phone Contact Number	Visit 1	Visit 2	Visit 3	Visit 4	Visit 5	Visit 6	Visit 7	Visit 8	Visit 9		Visit 10	Visit 11		
Screening/Baseline:														
Inclusion/Exclusion ²	X	X	X											
Main study informed consent	X													
Genomics sub-study informed consent ³	X													
Medical history	X													
Medication history	X													
Demographics	X													
Diary instructions		X	X											
Training on pain reporting /patient education brochures ⁴	X	X												
MRI for index joint, contralateral joint & any hip or knee with K-L ≥3	X													
Randomization			X											
Treatment:														
Discontinue non-study pain medications		X												
Study drug SC injection ⁵			X			X	X	X						

	Screening/Pre-randomization		Treatment Period							Follow-up Period			EOS	
Study Week	Screen	Pre-rand	Baseline	Wk 1	Wk 2	Wk 4	Wk 8	Wk 12	EOT Wk 16	ET ¹ / JR Pre-Op	Wk 26	Wk 36	ET ¹ / JR Pre-Op	Wk 64
Study Day	Up to 30 Days	7 to 10 Days	1	8	15	29	57	85	113		183	253		449
Visit Window (days)				±1	±3	±7	±7	±7	±7		±7	±7		
Visit/Phone Contact Number	Visit 1	Visit 2	Visit 3	Visit 4	Visit 5	Visit 6	Visit 7	Visit 8	Visit 9		Visit 10	Visit 11		Phone 1
Dispense to home paracetamol/acetaminophen		X	X			X	X	X						
Paracetamol/acetaminophen accountability			X		X	X	X	X	X	X				
Record rescue medication use in diary ⁶		X	X	X	X	X	X	X	X	X				
Concomitant therapies	X	X	X	X	X	X	X	X	X	X	X	X	X	
Patient-Completed Assessments/Efficacy:														
WOMAC ^{7, 22}	X ⁷		X		X	X	X	X	X	X	X	X	X	
Neurological Assessments:														
Nerve conduction	X ⁸						X		X	X ⁹		X	X ⁹	
Neurological examination (full)	X		X		X	X	X	X	X	X	X	X	X	
Survey of autonomic symptoms ²²	X		X		X	X	X	X	X	X	X	X	X	
Orthostatic blood pressure assessment and heart rate ^{10,11}	X	X	X		X	X	X	X	X	X	X	X	X	
Safety:														
Vital signs ¹¹	X		X		X	X	X	X	X	X	X	X	X	
Electrocardiogram	X								X	X				
Physical examination and weight	X								X	X		X	X	
Joint pain questionnaire ²²	X		X		X	X	X	X	X	X	X	X	X	
Event-triggered imaging ¹²				X	X	X	X	X	X	X	X	X	X	
Adverse Events	----->													
SC injection site evaluation			X			X	X	X						

	Screening/Pre-randomization		Treatment Period								Follow-up Period			EOS
Study Week	Screen	Pre-rand	Baseline	Wk 1	Wk 2	Wk 4	Wk 8	Wk 12	EOT Wk 16	ET ¹ / JR Pre-Op	Wk 26	Wk 36	ET ¹ / JR Pre-Op	Wk 64
Study Day	Up to 30 Days	7 to 10 Days	1	8	15	29	57	85	113		183	253		449
Visit Window (days)				±1	±3	±7	±7	±7	±7		±7	±7		
Visit/Phone Contact Number	Visit 1	Visit 2	Visit 3	Visit 4	Visit 5	Visit 6	Visit 7	Visit 8	Visit 9		Visit 10	Visit 11	Phone 1	
Bilateral X-rays (knee, hip, shoulder)	X ¹³								X	X		X	X	
Pre-op questionnaire (JR follow-up) ¹⁴										X			X	
MRI affected joint(s) - AA patients only ¹⁵														X
End of study phone contact ¹⁶														X
Laboratory Testing:														
Urine drug test ¹⁷	X													
Hematology ¹⁷	X					X		X	X	X	X	X	X	
Blood chemistry ¹⁷	X					X		X	X	X	X	X	X	
Urinalysis and urine electrolytes ¹⁷	X					X		X	X	X	X	X	X	
ESR	X													
HbA1c ¹⁷	X													
FSH and estradiol ^{17,18}	X													
Pregnancy test (for WOCBP) ¹⁹	X - Serum		X - Urine			X - Urine	X - Urine	X - Urine	X - Urine					
PK, Antibody, and Research Samples:														
PK sample ²⁰			X	X	X	X	X	X	X	X		X	X	
ADA samples ²⁰			X						X	X		X	X	
Genomics sub-study sample (optional) ³			X											
hs-CRP sample ^{20,21}			X			X			X	X		X	X	
Research serum/plasma sample ^{20,21}			X			X			X	X		X	X	

AA: Adjudicated arthropathy
 ADA: Anti-drug antibody
 EOS: End of study
 EOT: End of treatment
 ESR: Erythrocyte sedimentation rate
 ET: Early termination
 FSH: Follicle stimulating hormone

JR: Joint replacement
 MRI: Magnetic resonance imaging
 PK: Pharmacokinetic
 Pre-op: Pre-operative
 Pre-rand: Pre-randomization
 SC: Subcutaneous
 Wk: Week

HbA1c: Glycated hemoglobin
hs-CRP: high-sensitivity C-reactive Protein

WOCBP: Women of childbearing potential
WOMAC: Western Ontario and McMaster Universities Osteoarthritis Index

Footnotes for Table 1 - Schedule of Events

1. Patients who discontinue study drug will be encouraged to follow the visit schedule throughout the entire study. If a patient chooses to end study participation he/she will be asked to return to the study site as soon as possible for an Early termination (ET) visit. Imaging assessments need to be repeated if it has been >30 days since the joints were last imaged. If it has been ≤30 days since imaging assessments were completed, imaging assessments may be completed at the discretion of the investigator.
2. HIV and/or hepatitis testing will be performed on a country-by-country basis, according to local guidelines if required by regulatory authorities or ethics boards. Patients must complete all other inclusion/exclusion assessments before undergoing the nerve conduction assessments.
3. Only for patients who provide written informed consent for the optional genomics sub-study. The sample should be collected at the day 1 (baseline/randomization) visit, but may be collected at any visit during the study after a patient has been randomized.
4. At the screening and pre-randomization visits, study staff will review the “Participating in a Research Study: What You Need to Know” brochure and the “Reporting Your Pain” brochure with patients to ensure they understand what a clinical study is and how to report their pain accurately. At subsequent visits, patients will be asked to review the ‘Reporting Your Pain’ brochure themselves. At any time during the conduct of the study, patients may require retraining by study staff.
5. Study drug administration will be the last procedure at each dosing visit, and will be administered after all laboratory, PK, ADA, and research samples have been collected and all study related activities have been performed. Patients will be observed in the clinic for approximately 1 hour after SC study drug is administered.
6. Use of study-provided rescue medication will be recorded daily using diaries. Acetaminophen/paracetamol use will be reported from pre-randomization visit to week 16.
7. The WOMAC pain sub-scale will be evaluated for both knees and both hip joints at the screening visit only. Then, the WOMAC Full Survey will be completed only for the index joint at the subsequent visits.
8. Nerve conduction can be performed during screening or pre-randomization. Patients must complete all other inclusion/exclusion assessments before undergoing the nerve conduction assessments. Randomization cannot occur until there is confirmation from the central reader assessment that the results are within the established parameters.
9. Nerve conduction assessments should be performed at the ET visit if it has been >2 weeks since the last nerve conduction assessment.

10. Blood pressure measurements to assess for orthostatic hypotension may be discontinued following regulatory approval if the safety database does not reveal an imbalance for the fasinumab-treated patients.
11. If the pulse is less than 45 bpm at any visit, an ECG with rhythm strip will be obtained and sent to the central reader to confirm the heart rate and rhythm.
12. Imaging (X-ray and/or MRI) will be performed at the investigator's discretion on any joint with worsening or exacerbation of pain beyond the fluctuations in pain typical for that patient's OA. This imaging will be submitted to the adjudication committee for review.
13. If screening radiographs are inconclusive for potential joint related findings, an MRI must be performed. Confirmation from the central reader that there are no exclusionary findings on the MRI must be received before a patient can be randomized.
14. In the event that a patient must undergo JR surgery during the study, the patient must complete the pre-operative visit (ET assessments, as applicable) and the procedures outlined in the schedule of events for JR follow-up. This will include a Knee Society Score questionnaire for knee replacements or Harris Hip Score questionnaire for hip replacements. The pre-operative visit must be completed before the JR surgery. Pre-operative images will be submitted to the adjudication committee for review.
15. If the AA joint(s) has undergone JR, an X-ray may be substituted for an MRI.
16. The purpose of this phone contact is to ask the patient if he/she has had or is scheduled (or on a waiting list) to have JR surgery. Pre-operative images will be submitted to the central reader for adjudication, if available.
17. Samples will be analyzed by the central laboratory and results will be evaluated by the investigator.
18. Assessment of FSH and estradiol levels are only to be performed if assessment of postmenopausal status is required (ie, for female patients ≤ 59 years of age).
19. In the event of a positive urine pregnancy test result, the patient must have a serum pregnancy test with a negative result in order to continue study drug. If the serum pregnancy test is positive, the patient must be withdrawn from study drug and should be asked to return to the clinic for all remaining study visits per the visit schedule.
20. Collection of samples for PK, ADA, and research are mandatory at the time points specified above. In addition, PK, ADA, and research samples may be drawn at any scheduled visit or unscheduled visit if a patient experiences a treatment-related safety TEAE. Samples should be collected prior to study drug administration on study drug dosing days.
21. Biomarker samples should be collected after the patients have been fasting overnight or for 8 hours (in the event of an afternoon visit).
22. Patient-reported outcome measures should be completed before any clinical assessments.

Table 2: Follow-up Period for Patients Undergoing Joint Replacement Surgery on Study

Follow-up Study Day (Visit Window) ¹	Post-Operative	Long-Term
	Follow-up Visit 1 4 weeks after joint replacement surgery	Follow-up Visit 2 20 weeks after joint replacement surgery
	Follow-up Day 29 (±5)	Follow-up Day 140 (±7)
Treatment:		
Concomitant medications and therapy	X	X
Safety:		
Adverse events	----->	
Vital signs	X	X
Orthostatic blood pressure ²	X	X
Physical examination with joint examination	X	X
Medical history related to the joint replacement	X	X
Joint pain questionnaire	X	X
Post-operative questionnaire ³	X	X
Bilateral X-rays (shoulders, hips, knees) ⁴	X ⁵	X
Event-triggered imaging ⁶	X	X

Footnotes for Table 2 - Follow-up Period for Patients Undergoing Joint Replacement Surgery

1. All available information for patients who undergo JR surgery must be collected, including placement of the prosthesis, healing of the surgical wound and the results of the histopathologic examination.
2. If it is not possible to obtain orthostatic blood pressure following JR then blood pressure and pulse should be recorded.
3. A Knee Society Score questionnaire for knee replacements or Harris Hip Score questionnaire for hip replacements.
4. In the event of more than 1 JR, imaging assessments should be repeated if it has been >60 days since the joints were last imaged. If it has been ≤60 days since imaging assessments were completed, imaging assessments may be completed at the discretion of the investigator. An MRI may be requested by the imaging vendor after review of the X-rays.
5. Imaging will be done at week 4 if not done pre-operatively.
6. Imaging may be performed on any joint following a report of clinically significant worsening or exacerbation of pain in that joint.

10.2. Reference for Criteria for Treatment-Emergent Potentially Clinically Significant Values (PCSV)

The PCSV criteria below should be used as a reference; the actual criteria for each study should be determined and agreed to by the study team prior to database lock as part of SAP and should be based on the study population, indication, and potential effects of study treatment.

Table 3: Criteria for Treatment-Emergent Potentially Clinically Significant Values (PCSV)

Parameter	Treatment Emergent PCSV	Comments
Clinical Chemistry		
ALT*	>3 and \leq 5 ULN and baseline \leq 3 ULN*	Enzyme activity must be expressed in ULN, not in IU/L.
	>5 and \leq 10 ULN and baseline \leq 5 ULN	FDA DILI Guidance July 2009.
	>10 and \leq 20 ULN and baseline \leq 10 ULN	Each category is calculated independently.
	>20 ULN and baseline \leq 20 ULN	* At least one level is required; multiple levels are optional for phase 2/3 studies. If it is desirable to get the distribution across the different PCSV levels, additional shift table on \leq 3, >3 to \leq 5, >5 to \leq 10, >10 to \leq 20, and >20 category for baseline vs. post baseline may be provided

Parameter	Treatment Emergent PCSV	Comments
AST*	
>3 and \leq 5 ULN and baseline \leq 3 ULN*
 
>5 and \leq 10 ULN and baseline \leq 5 ULN
 
>10 and \leq 20 ULN and baseline \leq 10 ULN
 
>20 ULN and baseline \leq 20 ULN
	
Enzyme activity must be expressed in ULN, not in IU/L.
 
FDA DILI Guidance July 2009.
 
Each category is calculated independently.
 
* At least one level is required; multiple levels are optional for phase 2/3 studies. If it is desirable to get the distribution across the different PCSV levels, additional shift table on \leq3, >3 to \leq5, > 5 to \leq10, >10 to \leq20, and >20 category for baseline vs. post baseline may be provided

Alkaline Phosphatase	>1.5 ULN and baseline \leq 1.5 ULN	
Enzyme activity must be expressed in ULN, not in IU/L.
 
FDA DILI Guidance July 2009.

Total Bilirubin*	
>1.5 and \leq 2 ULN and baseline \leq 1.5 ULN*
 
>2 ULN and baseline \leq 2.0 ULN
	
Must be expressed in ULN, not in μmol/L or mg/L. Categories are cumulative.
 
FDA DILI Guidance July 2009.
 
* At least one level is required; multiple levels are optional for phase 2/3 studies. If it is desirable to get the distribution of significant level, additional shift table on \leq1.5, >1.5 to \leq2.0 and > 2.0 category for baseline vs. post baseline may be provided

Parameter	Treatment Emergent PCSV	Comments
Conjugated Bilirubin	(Direct Bilirubin >35% Total Bilirubin and Total Bilirubin >1.5 ULN) and (Direct Bilirubin <=35% Total Bilirubin or Total Bilirubin <=1.5 ULN) at baseline	Conjugated bilirubin dosed on a case-by-case basis.
ALT/AST and Total Bilirubin	(ALT >3 ULN and TBILI>2 ULN) and baseline (ALT <=3 ULN or TBILI <=2 ULN) (AST >3 ULN and TBILI>2 ULN) and baseline (AST <=3 ULN or TBILI <=2 ULN) (ALT >3 ULN and TBILI>1.5 ULN) and baseline (ALT <=3 ULN or TBILI <=1.5 ULN) (AST >3 ULN and TBILI>1.5 ULN) and baseline (AST <=3 ULN or TBILI <=1.5 ULN)	FDA DILI Guidance July 2009.
ALT/AST and Total Bilirubin and ALP	(ALT >3 ULN and TBILI>2 ULN and ALP < 2 ULN) and baseline (ALT <=3 ULN or TBILI <=2 ULN or ALP >=2 ULN) (AST>3 ULN and TBILI>2 ULN and ALP < 2 ULN) and baseline (AST <=3 ULN or TBILI <=2 ULN or ALP >=2 ULN)	FDA DILI Guidance July 2009.

Parameter	Treatment Emergent PCSV	Comments
CPK*	>3 and \leq 10 ULN and baseline \leq 3ULN*	FDA Feb 2005.
	>10 ULN and baseline \leq 10ULN	Am J Cardiol April 2006.
		Categories are cumulative. * At least one level is required; multiple levels are optional for phase 2/3 studies. If it is desirable to get the distribution of significant level, additional shift table on \leq 3, >3 to \leq 10, and > 10 category for baseline vs. post baseline may be provided
Creatinine	\geq 150 μ mol/L (Adults) and baseline < 150 μ mol/L	Benichou C., 1994
	\geq 30% change from baseline and <100% change from baseline	3 independent criteria
	\geq 100% change from baseline	
Uric Acid		Harrison - Principles of internal Medicine 17 th Ed., 2008.
Hyperuricemia	>408 μ mol/L and \leq 408 μ mol/L at baseline	Two independent criteria
Hypouricemia	<120 μ mol/L and \geq 120 μ mol/L at baseline	
Blood Urea Nitrogen	\geq 17 mmol/L and <17 mmol/L at baseline	Two independent criteria

Parameter	Treatment Emergent PCSV	Comments
Chloride		Two independent criteria
Hypochloremia	<80 mmol/L and baseline \geq 80 mmol/L	
Hyperchloremia	>115 mmol/L and baseline \leq 115 mmol/L	
Sodium		Two independent criteria
Hyponatremia	\leq 129 mmol/L and baseline > 129 mmol/L	
Hypernatremia	\geq 160 mmol/L and baseline <160 mmol/L	
Potassium		FDA Feb 2005.
Hypokalemia	<3 mmol/L and baseline \geq 3 mmol/L	Two independent criteria
Hyperkalemia	\geq 5.5 mmol/L and baseline <5.5 mmol/L	
Total Cholesterol	\geq 7.74 mmol/L and < 7.74 mmol/L at baseline	Threshold for therapeutic intervention.
Triglycerides	\geq 4.6 mmol/L and < 4.6 mmol/L at baseline	Threshold for therapeutic intervention.
Glucose		
Hypoglycaemia	(\leq 3.9 mmol/L and <LLN) and (>3.9 mmol/L or \geq LLN) at baseline	ADA May 2005.
Hyperglycaemia	\geq 11.1 mmol/L (unfasted); \geq 7 mmol/L (fasted) and < 11.1 mmol/L (unfasted); <7 mmol/L (fasted) at baseline	ADA Jan 2008.
HbA1c	>8% and \leq 8% at baseline	

Parameter	Treatment Emergent PCSV	Comments
Albumin	≤25 g/L and >25 g/L at baseline	
hs-CRP	2 ULN or > 10 mg/L (if ULN not provided)	FDA Sept. 2005
Hematology		
WBC	<3.0 Giga/L and ≥3.0 Giga/L at baseline (Non-Black); Increase in WBC: not relevant. <2.0 Giga/L and ≥2.0 Giga/L at baseline (Black) ≥16.0 Giga/L and < 16 Giga/L at baseline	To be interpreted only if no differential count available.
Lymphocytes	>4.0 Giga/L and ≤ 4.0 Giga/L at baseline	
Neutrophils	<1.5 Giga/L and ≥1.5 Giga/L at baseline (Non-Black); <1.0 Giga/L and ≥1.0 Giga/L at baseline (Black)	International Consensus meeting on drug-induced blood cytopenias, 1991. FDA criteria.
Monocytes	>0.7 Giga/L ≤ 0.7 Giga/L at baseline	
Basophils	>0.1 Giga/L ≤ 0.1 Giga/L at baseline	
Eosinophils	(>0.5 Giga/L and >ULN) and (≤0.5 Giga/L or ≤ ULN at baseline)	Harrison - Principles of internal Medicine 17 th Ed., 2008.

[figure not shown]
Parameter	Treatment Emergent PCSV	Comments
Hemoglobin	
≤ 115 g/L and > 115 g/L at baseline for male; ≤ 95 g/L and > 95 g/L at baseline for Female. ≥ 185 g/L and < 185 g/L at baseline for Male; ≥ 165 g/L and < 165 g/L at baseline for Female Decrease from Baseline ≥ 20 g/L
	
Three criteria are independent.
 
Criteria based upon decrease from baseline are more relevant than based on absolute value. Other categories for decrease from baseline can be used (≥ 30 g/L, ≥ 40 g/L, ≥ 50 g/L).

Hematocrit	
≤ 0.37 v/v and > 0.37 v/v at baseline for Male; ≤ 0.32 v/v and > 0.32 v/v at baseline for Female ≥ 0.55 v/v and < 0.55 v/v at baseline for Male; ≥ 0.5 v/v and < 0.5 v/v at baseline for Female
	Two Criteria are independent
RBC	
Female < 3 Tera/L and baseline ≥ 3 Tera/L ≥ 6 Tera/L and baseline < 6 Tera/L
 
Male < 4 Tera/L and baseline ≥ 4 Tera/L ≥ 7 Tera/L and baseline < 7 Tera/L
	
Unless specifically required for particular drug development, the analysis is redundant with that of Hb.
 
Otherwise, consider FDA criteria.

Parameter	Treatment Emergent PCSV	Comments
Platelets	<100 Giga/L and \geq 100 Giga/L at baseline	International Consensus meeting on drug-induced blood cytopenias, 1991. Two independent criteria
	\geq 700 Giga/L and < 700 Giga/L at baseline	
Urinalysis		
pH	\leq 4.6 and > 4.6 at baseline	Two independent criteria
	\geq 8 and < 8 at baseline	
Vital signs		
HR	\leq 50 bpm and decrease from baseline \geq 20 bpm	To be applied for all positions (including missing) except STANDING.
	\geq 120 bpm and increase from baseline \geq 20 bpm	
SBP	\leq 95 mmHg and decrease from baseline \geq 20mmHg	To be applied for all positions (including missing) except STANDING.
	\geq 160 mmHg and increase from baseline \geq 20 mmHg	
DBP	\leq 45 mmHg and decrease from baseline \geq 10 mmHg	To be applied for all positions (including missing) except STANDING.
	\geq 110 mmHg and increase from baseline \geq 10 mmHg	

Parameter	Treatment Emergent PCSV	Comments
Orthostatic Hypotension	Su SBP < 160 mmHg -	
	SBP St – Su ≤ - 20 mmHg	
	DBP St – Su ≤ - 10 mmHg	
	Su SBP ≥ 160 mmHg -	
	SBP St – Su ≤ - 30 mmHg	
	DBP St – Su ≤ - 15 mmHg	
Weight	≥5% increase from baseline	FDA Feb 2007.
	≥5% decrease from baseline	
ECG		Ref.: CPMP 1997 guideline. ICH E14 2005
HR	≤50 bpm and decrease from baseline ≥20 bpm	
	≥120 bpm and increase from baseline ≥20 bpm	
PR	≥220 ms and increase from baseline ≥20 ms	
QRS	≥120 ms & < 120 ms at baseline	

Parameter	Treatment Emergent PCSV	Comments
QTc	Absolute values (ms) >450 ms and baseline <=450 ms >480 ms and baseline <=480 ms >500 ms and <= 500 ms at baseline Increase from baseline Increase from baseline 30-60 ms Increase from baseline >60 ms	To be applied to any kind of QT correction formula. $\Delta QTc > 60$ ms are the PCSA to be identified in individual subjects/patients listings.

